Contact for Clinical Queries	
[name]* Mersey & West Lancashire Teaching Hospitals NHS Trust, Diabetes Centre St Helens Hospital [name]
 
PA: [name] Email: [contact]

Sponsor	
The University of Liverpool is the research Sponsor for this Study. It is recognised that as an employee of the University the Chief Investigator has been delegated specific duties, as detailed in the Sponsorship Approval letter.
 
For further information regarding the sponsorship conditions, please contact:
 
[name] Senior Clinical Research Governance Manager [contact]

Key Protocol Contributors	
[name]* Email: [contact]
 
[name]* Email: [contact]

Committees	
This research proposal will be submitted to IRAS for independent ethical opinion by the Health Research Authority.
 
University of Liverpool Committee on Research Ethics** (online ethical approval process completed – confirmed that IRAS approval required)

*CV in appendix 1. ** University of Liverpool research ethics application project ID 13707.

Study Summary

Study Design	Quantitative feasibility study
Study Participants	People with type 2 diabetes mellitus
Planned Size of Sample (if applicable)	
120 people with type 2 diabetes.
 
Participants will be randomised across four groups, each with 30 participants.

Follow up duration (if applicable)	4 months
Planned Study Period	
This is educational research which is being undertaken to fulfil the requirements of a 3-year full time PhD with University of Liverpool commencing November 2023.
 
GANNT chart detailing timetable of research activities in appendix

	1.
Research Question/Aim(s)	
Aims
 
Using a quantitative approach this feasibility study aims to explore if patients who attend minimal aspects (10%) of diabetes self-management education (DSME) programmes gain clinically significant improvements in ability to self-care compared to those who do not attend. If the nationally accepted 60 % completion rate is as effective as 100% completion, and if
 
Research question
 
1. What is the impact of differing completion rates of DSME programmes on ability to self-care (primary outcome), diabetes distress and health related quality of life in type 2 diabetes.

Abstract

Background: Structured diabetes self-management education (DSME) is internationally recommended for all people with newly diagnosed type 2 diabetes and is designed to support patients in self-managing their condition and prevent associated long-term complications. DSME is proven to be as effective as pharmacotherapy in preventing diabetes associated morbidity and premature mortality but attendance at both a national and local level remains poor. Local records suggest that of those that start DSME (9%) only 12.6% complete the programme. Attendance at DSME is currently benchmarked as having completed a registration form and had at least one active engagement with a programmes content, with 'completion' measured against ≥60% completion despite landmark trials reporting outcomes based on the full completion of a programme. Little is known, of the effectiveness of DSME on the psychological and emotional health of people with diabetes who complete less than the full DSME programme.

Aim: This feasibility study will test the impact of differing completion rates of a face-to-face DSME programme on patient reported outcomes measuring self-care, diabetes distress and quality of life in people with type 2 diabetes.

Methods: Using a quantitative approach, a single centre, randomised feasibility study will be conducted, aiming to recruit 120 eligible people with type 2 diabetes due to attend a secondary care diabetes clinic in the Northwest UK for specialist support, education and advice. Participants will be randomised into one of four groups: Group 1 will receive a full DSME programme, Group 2 will receive 60%, Group 3 will receive 10% and Group 4 will have delayed education. Normal clinical care will continue. Preliminary outcomes (psychometric questionnaire scores measuring ability to self-care, diabetes distress and health related quality of life) will be evaluated at baseline and 3-4 months post-intervention. Measures of feasibility (eligibility, recruitment and retention rates) will be

reported.

Original contribution to knowledge: Whilst the current literature evidences the clear benefits for people with type 2 diabetes attending DSME programmes, there is minimal understanding of the benefits of partial DSME completion on a person's ability to self-care despite national consensus accepting 60% attendance as 'completed'. The proposed research aims to test the feasibility of conducting a full randomised control trial to evaluate the effectiveness of DSME programmes on psychometric outcomes with differing completion rates.

Lay Summary

Type 2 diabetes accounts for 90% of all diabetes diagnoses. Without proper care, type 2 diabetes can result in complications such as stroke, heart disease, kidney disease, eye disease and nerve damage. On average, a person with diabetes spends less than three hours a year with a healthcare professional meaning patients must manage their own diabetes almost 100% of the time. Diabetes self-management education plays an important role in helping people stay healthy, live well, and avoid life threatening complications and is proven to be effective in lowering blood glucose levels and preventing health problems later in life. Despite an increased awareness of the importance of education for people with type 2 diabetes, attendance at education programmes remains very poor with little to no change over the past decade.

Many things can prevent attendance or completion of education programmes, including physical and mental health issues, reduced finances, work and childcare commitments, location of education programmes and lack of information on programme content or availability. Little is known on the effectiveness of only attending part of an education programme on a person's ability to self-care.

This study will examine the impact of differing completion rates of diabetes self-management education programmes on a person's self-care skills. The psychological impact of not completing a diabetes self-management education programme is unknown and a better understanding of this could help tailor future education offers for people with type 2 diabetes. This is a smaller study to see if a larger project is feasible in the future.

Funding and Support in Kind

FUNDER(S)	FINANCIAL AND NON-FINANCIAL SUPPORT GIVEN
Department of Endocrinology and Diabetes, St Helens Hospital, Mersey and West Lancashire Teaching Hospitals NHS Trust.	Funded clinical research fellow post and PhD fees at University of Liverpool. Postage costs for patient information sheets to patients

Roles and Responsibilities of Study Sponsor and Funder

The sponsor of this study is University of Liverpool where the researcher is currently registered on her full-time

3-yr PhD. The University of Liverpool is a member of the prestigious Russell Group of UK research intensive institutions and is internationally recognised with 91% of its research being ranked as world-leading and internationally excellent in the latest Research Excellence Framework. As the study sponsor, the University of Liverpool is responsible for the initiation and management of the research and takes primary responsibility for ensuring that the design of the study meets appropriate standards.

The funder is the Diabetes Centre, St Helens Hospital, Mersey and West Lancashire Teaching Hospitals NHS Trust who will provide the working environment and resources for the clinical research fellow post to which the researcher is employed.

Service user involvement

The DIABETES-PRO study design and justification have been discussed with a service user living with diabetes. Having completed previous education programmes they were shocked by the low number that attend DSME programmes and that a record of 'attended' required minimal engagement with a programme, or that a patient is classes as 'completed' following engagement with >60% of a programme. The service user was reassured that all patients would be offered a full education programme at the end of the study and thought the offer of a home visit or telephone appointment to reduce the burden on patients to attend an additional appointment at the end of the study (follow up visit) was important.

Templates from the Health Research Authority (HRA) have been adopted for use in this study to ensure that participant information sheets and consent forms are easy to read and contain the required information to support participants in making an informed choice.

Peer review

Peer review has been completed and submitted to the sponsor. Copies of peer review feedback is included in Appendix 1. The internal peer reviewer (Consultant Physician/Diabetologist) and external peer reviewer (Physiotherapy Lecturer and Researcher) both approved the study. Comments are summarised below, with accompanying amendments.

1. Clarify the role of the researcher in supporting participants (minor). Section 6.2 Study processes updated and Section 9 Adverse events updated to include table 5.

Protocol Contributors

Author of the protocol: [name]

Supervision / advice: [name], [name], [name].

[figure not shown]
The PhD student will undertake this research as part of a research PhD at the University of Liverpool. The study sponsor (University of Liverpool) and funder (Mersey and West Lancashire Teaching Hospitals NHS Trust) will

control the final decision on study design, conduct, data analysis and interpretation , manuscript writing and dissemination of results.

James Lind Alliance top 10 priorities for type 2 diabetes have informed the aims and objectives for this research protocol (1).

Key Words: type 2 diabetes mellitus; patient education as topic; patient reported outcome measures; health education;

Study Flow Chart

[^]People newly diagnosed with type 2 diabetes in primary care receive a snowmed code recording their diagnosis on EMIS, this is reported via a shared care report which is used to offer DSME by the specialist diabetes centre which is also the DSME provider.

*At the end of the study participants in groups 2, 3 and 4 will be offered a full DSME programme.

Figure 1: Study flow chart

Glossary of Abbreviations

HRA	Health Research Authority
REC	Research Ethics Committee
PIS	Participant Information Sheet
DSME	Diabetes Self-Management Education
PRO	Patient Reported Outcome
PROM	Patient Reported Outcome Measure
MCID	Minimal Clinically Important Difference
QISMET	Quality Institute for Self-Management Education and Training
HCPC	Health and Care Professions Council
HEA	Higher Education Academy
NICE	National Institute of Clinical Excellence

Contents

Research Reference Numbers	1
Signature Page	2
Key Study Contacts	3
Study Summary	4
Funding and Support in Kind	6
Roles and Responsibilities of Study Sponsor and Funder	6
Protocol Contributors	7
Key Words:	8
Study Flow Chart	9
Glossary of Abbreviations	10
INTRODUCTION	13
BACKGROUND	13
RATIONALE FOR CURRENT STUDY	16
THEORECTICAL FRAMEWORK	17
4.1 Null hypothesis	17
RESEARCH QUESTION	18

Diabetes is a complex condition leading to increased disability and premature mortality; 7000 excess deaths in the United Kingdom in 2022 (2). The International Diabetes Federation (IDF) estimate 537 million people are living with diabetes around the world (3) of whom approximately 4.3 million reside in the UK (4). Over 90% of diagnoses are attributed to type 2 diabetes with an increased prevalence in areas with high levels of deprivation, poor access to healthcare, poorer housing, reduced finances, and lower levels of educational attainment (5). Presentation and disease progression of type 2 diabetes are heterogeneous, which can lead to delayed diagnosis, multiple abnormalities, and varying susceptibility to complications (6). Complications are often classified as either microvascular, such as retinopathy, neuropathy, and nephropathy, or macrovascular including cardiovascular, cerebrovascular, and peripheral vascular disease (7).

Diabetes prevalence in the UK has generally increased year on year since 2010/11 from less than 5% (8) to more than 7.3% in 2022/23 (9). Public Health England identified the most common causes of morbidity in 2019 according to global burden of disease, as measured by age standardised years lived with disability (YLDs) per 100,000 population, with diabetes accounting for the second main cause in males (figure 2), and the seventh main cause of morbidity in females (figure 3) (8). The YLD rate for diabetes mellitus increased significantly between 1990 and 2019 (males >2.3, females >2.2) (8). In 2019 the USA had the highest burden of all cause morbidity in both males and females followed by England (and the UK), while Japan had the lowest, England had the highest rate of morbidity for diabetes in males and second highest for diabetes in females (8). Whilst mortality specifically linked to diabetes has decreased (10), emergency admissions have increased more rapidly in areas of high deprivation when compared to those in the least deprived quintiles (11). Increased incidence of diabetes is associated with Black and Asian ethnicity (12,13) and lower socio-economic status [17,18] which is associated with poorer outcomes and poorer compliance with diabetes treatments [19], including engagement with DSME [20] and a significantly greater mortality rate (14).

[figure not shown]

Figure 2: Male common causes of morbidity in England 2019 (8)

[figure not shown]

Figure 3: Female common causes of morbidity in England 2019 (8)

[figure not shown]
NICE recommends DSME is offered at the point of diagnosis and annually thereafter for people with type 2 diabetes (15). Despite this, uptake of DSME remains poor (table 1) (9) with a discord between offered and attended figures at a local and national level with evidence suggesting DSME is equally as important as pharmacotherapy in the effective management of type 2 diabetes (15–17). Negative perceptions of education remain an obstacle to adult learning and the uptake of DSME [22] despite a joint consensus by the American Diabetes Association (ADA) and European Association for the Study of Diabetes (EASD) (18) and NICE (15) all considering DSME as the foundation for successful management of diabetes, and for avoidance of associated metabolic co-morbidities and hospitalisation (19).

Table 1: DSME figures of offer and attended within 12 months of diagnosis (9)

DSME within 12 months of diagnosis	St Helens %	England %
Offered	68.9	71.0
Attended	9.1	7.0

The National Diabetes Audit suggests 71% of people with type 2 diabetes are offered DSME, with an average attendance rate of 7%. Local records suggest that of those that start DSME (9%) only 12.6% complete the programme (20), with those in a lower socioeconomic group harder to reach despite often needing the intervention the most (21). Multiple studies have demonstrated poor attrition rates across DSME programmes meaning patients frequently do not receive the required number of hours or content (21,22). NHS England (23) and the Center for Disease Control and Prevention (24) currently benchmark DSME attendance as completed a registration form and had at least one active engagement with a programmes content, with completion measured against $\geq 60\%$ despite landmark trials (23,25–27) reporting outcomes based on full completion of a programme. Evidence suggests the reasons for non-attendance and non-completion of DSME are multifactorial (28–31), with patients living in areas of high deprivation more likely to decline DSME programmes (30,32,33).

The borough of St Helens has a legacy of poor health linked with deprivation and the town's industrial past. St Helens is ranked as the 26th most deprived local authority in England, its relative position having deteriorated since 2015 with almost 25% of residents living in the 10% most deprived neighbourhoods in the country (34). St Helens has widespread health deprivation with a higher-than-average diabetes prevalence of 9.2% (14,935 individuals) (20), versus 7.3% in England (35). Despite improvements in mortality rates over the last 20 years the borough's mortality rate remains higher than the national average as seen in figure 4 (36), with two thirds of adults recorded as overweight or obese, 1 in 5 adults are physically inactive and less than 50% eat the recommended '5 a day' (37).

Source: NHS Digital. Primary Care Mortality Database (PCMD) *2018 & 2019 St Helens figures are provisional

Figure 4: All-age all-cause mortality trend 1999-2019 (36)

RATIONALE FOR CURRENT STUDY

Despite the current literature evidencing the clear benefits of DSME on behavioural choices, HbA_{1c} levels and reduced risk of morbidity and premature mortality (38) attendance and completion levels remain poor. There is minimal understanding of the impact of non-completion of DSME programmes on HbA_{1c} or psychometric outcomes. Positive endpoints for DSME studies are typically based on participants who complete the full programme (22) with HbA_{1c} (39) used as a measure of effectiveness yet often studies fail to demonstrate significant or lasting results despite being statistically powered (38).

There is scarce literature examining the impact of attrition on DSME effectiveness. Although a small retrospective study in the USA using secondary data analysis of 105 patient records reported patients who attended 1 or 8 hours or more of DSME had a significant reduction in HbA_{1c} when compared to those who received no education (22). Evidence is available looking at diabetes prevention programmes which suggests each session attended is linked to a reduction in body weight between 0.26-0.3% (24,40) suggesting a positive impact with any level of engagement.

Internationally the benchmark for recording a patient as completed DSME is attendance at $\geq 60\%$ of a programme's content (23,41–43), a discord with the literature measuring effectiveness of landmark studies at 100% completion (25,39). A record of DSME attendance is given for patients who sign up and engage with $>10\%$ of materials (23,41,43).

There is no research available measuring the impact of non-completion on UK DSME programme effectiveness or internationally on the impact of differing completion rates on patient reported outcome measures (PROMs) despite the acceptance of completion ($\geq 60\%$) at discord with legendary studies benchmarking completed at 100%. The aims of this study are to explore if patients who attend minimal aspects (10%) of DSME programmes gain clinically significant improvements in ability to self-care compared to those who do not attend, and if the nationally accepted 60 % completion rate is as effective as 100% completion.

THEORETICAL FRAMEWORK

Philosophical assumptions (also referred to as epistemology) influence our views about how phenomena should be approached (44) assisting researchers in refining the types of evidence required, how it should be collected, and how it should be interpreted. This quantitative study will adopt an experimental hypothesis driven design whereby the variable or intervention is controlled, with the exception of a control group, to attempt to establish causal effect of an intervention, in this case DSME completion rates. Whilst the most powerful and highly regarded form of experimental study remains the randomised control trial (RCT), this study will test the feasibility of conducting a full RCT.

This study positions itself with critical realism, often thought to be a useful middle ground between the naive realism associated with quantitative research 'what you see is what you get' and the subjectivity given to interpretive sciences. (45). Quantitative critical theory approaches are growing, complementing the objectivity afforded to quantitative designs with a social lens which considers social determinants of health. Whilst with any scientific method in which hypothesis are formulated there are inherent limitations, among them the problem of induction which prevents researchers from generalising observations on a select sample to the wider population, a fatal flaw in the logic of scientific research as the implication is nothing can be certain. Philosopher Karl Popper in 1935 acknowledged that whilst induction is a flaw in scientific research, the focus should not be in attempting to prove theories but trying to disprove them (46). The harder a researcher tries to disprove the null hypothesis the more confidence a reader should have in it (45). The DIABETES-PRO study focus is not in discovering new health care interventions but merely to test current interventions with small samples and generalising through the logic of induction and sophisticated statistical tests to measure and compare the efficacy of differing DSME completion rates for people with type 2 diabetes by translating variables into numerical data, a method often thought to be reductionist by nature (47).

4.1 Null hypothesis

Differing DSME completion rates have no impact on a person's ability to self-care, diabetes distress or health related quality of life.

RESEARCH QUESTION

Using a quantitative approach this feasibility study aims to explore if patients who attend minimal aspects (10%) of DSME programmes gain clinically significant improvements in ability to self-care compared to those who do not attend, and if the nationally accepted 60 % completion rate is as effective as 100% completion on patient reported outcome measures.

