5.1 Research question

1. What is the impact of differing completion rates of DSME programmes on ability to self-care (primary outcome), diabetes distress and health related quality of life in type 2 diabetes.

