6.1 Design

This is a single-centre randomised feasibility study evaluating the impact of different completion rates of DSME programmes on psychometric outcomes specifically looking at ability to self-care, diabetes distress and quality of life. DSME will be the intervention and will typically be delivered within 3 weeks of the baseline appointment. There is a deliberate short separation between education intervention and follow up psychometric tests of 3-4 months to allow participants the opportunity to adopt any behaviour changes following the DSME programme whilst minimising the risk of not receiving the full NICE recommended DSME programme and to broadly align with landmark studies. Landmark studies namely DCCT (26,27) and DESMOND (25) evidenced a statistically

significant improvement to PROMs at 4 months post education intervention, however HbA_{1c} changes were not significant within this timeframe despite being statistically powered. A recent systematic review (38) concluded that as DSME is primarily focused on behavioural change to facilitate glycaemic control, efficacy measures should focus on behavioural and psychosocial changes, however these are often overlooked. This study is a feasibility trial and by its very nature is not statistically powered, therefore despite HbA_{1c} being arguably the measure of choice within the literature for measuring effectiveness of diabetes interventions, this study will use PROMs as its primary outcome measure.

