6.4 Data Analysis

Descriptive analysis will be completed for all demographic data presenting continuous variables as means \pm standard deviation and categorical variables as numbers (%). Data will be tested for normality using a Shapiro-Wilk test and subject to visual inspection of histograms and normal Q-Q plots.

Psychometric outcomes will include the Diabetes Self-Management Questionnaire-Revised (DSMQ-R)(48), Problem Areas in Diabetes (PAID) scale (49) and the Patient reported outcome measures information system (PROMIS) Global Health scale v1.2 (50). Data will be treated as continuous and analysis of the difference in the mean before and after intervention will be conducted using an analysis of variance (ANOVA) test to check for statistical and clinical difference in the mean across the four groups.

Statistical analysis will be conducted using IBM® SPSS® Premium 29 with support from University of Liverpool statisticians. The alpha level will be set at 5% for statistical significance.

Whilst a statistically significant difference is desirable, it is important to understand what would represent a meaningful clinical change for a patient. As such the minimal clinically important difference (MCID) will be reported to measure the smallest difference in which the patient would perceive a benefit (61–64). Where the MCID is not published this will be calculated using a distribution-based derivation using 0.5 SD of the observed change in PROM score (62,65). Whilst this approach is not without its limitations (61,63) no consensus on the ideal means of determining the MCID is available (63). A systematic review concluded that 0.5 SD of the observed change approximated the published MCID in the majority of cases popularising this derivation in the literature (65).

MCID will be classed as >2 T-score points for the PROMIS Global Health v1.2 (66) in which physical health and mental health are given separate T-scores with a 95% confidence interval. The MCID will be calculated for PAID and DSMQ-R.

Recruitment of participants and the number of dropouts will be reported descriptively (frequencies and percentages). Due to the aims of this study considering differing completion levels of DSME, intention to treat analysis will not be used. Where participants allocated to a group do not fully complete the required amount of DSME there results would be withdrawn from the final analysis.

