8.2 Recruitment

8.2.1 Sample Size

A sample size of 24-50 participants per group is deemed adequate within a feasibility study to estimate effect sizes and inform future DSME modifications and research (68,69). A sample of 120 patients will be enrolled onto this study allowing for adequate numbers (n=30) across the four groups, controlling for expected participant drop out. Monthly recruitment targets are pre-specified in a study progression criteria table (table 3) to ensure an adequate sample size is achieved for data analysis.

The diabetes outpatient department receives on average 24 referrals for DSME per month with a mean monthly attendance rate of 21 patients. Locally an average of 86 patients are newly diagnosed with type 2 diabetes each month (20), patients who have opted in for data sharing are contacted with an offer of DSME. This has been used to inform realistic recruitment rates. Recruitment rates will be kept under review and discussed with supervisors should the monthly figure fall below projected numbers.

Table 3:Progression criteria and study status

Criterion	Green	Amber	Red
Monthly recruitment	≥ 17 participants	14-16 participants	< 13 participants
Retention rate	>80% at endpoint	60-80% at endpoint	<60% at endpoint

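### The aims name two pairwise comparisons (10% v none; 60% 'as effective as' 100%), but section 6.4 plans only a four-group ANOVA of difference, which isolates neither and cannot show similarity

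*Combined protocol and SAP*

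**What the plan says.** The Study Summary, the Rationale and section 5 (Research Question) give the same two aims. The first is whether people who attend 10% of the programme "gain clinically significant improvements in ability to self-care compared to those who do not attend". The second is "if the nationally accepted 60 % completion rate is as effective as 100% completion on patient reported outcome measures". In terms of the randomised groups, aim 1 is Group 3 (10%) against Group 4 (delayed education), and aim 2 is Group 2 (60%) against Group 1 (100%).

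The formal hypothesis in section 4.1 is a global null: "Differing DSME completion rates have no impact on" self-care, distress or quality of life. The numbered question in 5.1 is similarly general: "What is the impact of differing completion rates of DSME programmes on ability to self-care", distress and quality of life.

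Section 6.4 names one inferential method, an ANOVA of before-to-after differences, as a "test to check for statistical and clinical difference in the mean across the four groups". It adds: "The alpha level will be set at 5% for statistical significance". It also plans to report an MCID: 0.5 SD of observed change for DSMQ-R and PAID, and more than 2 T-score points for PROMIS. It names no planned contrast, post hoc test, between-group confidence interval or similarity margin. The only interval it mentions is for the PROMIS T-scores.

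Section 6.1 states: "This study is a feasibility trial and by its very nature is not statistically powered". Section 8.2.1 says that 24-50 per group "is deemed adequate within a feasibility study to estimate effect sizes and inform future DSME modifications and research".

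**The concern.** The ANOVA fits the global null in 4.1 and the general question in 5.1, but neither aim. Its F statistic pools all departures from equality among four means. A significant result does not say whether 10% differs from none, or 60% from 100%.

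Aim 2 has a second difficulty because it is a question of similarity. A test of difference has equality as its null, so failing to reject does not support equality, least of all in a study declared unpowered. The protocol does not say that p>0.05 will be read as 'as effective', but it does not rule this out, and the wording of aim 2 leaves that reading open.

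At stake are the report of the two aims and the between-group estimates carried into the full trial. The sample is justified by its ability to estimate effects, yet 6.4 does not say which between-group differences will be estimated or with what precision. The progression criteria in Table 3 (recruitment and retention) are not affected.

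**Working it through.** **Inputs from the protocol.** There are four groups of 30 (Study Summary, 8.2.1), and 4 × 30 = 120, as stated. There is no power calculation to reproduce. Alpha is 5% (6.4). Retention boundaries in Table 3 are 80% and 60%, giving 30 × 0.80 = 24 and 30 × 0.60 = 18 per group.

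**Assumptions.** The documents give no SD and no expected effect, so everything is in units of 1 SD of change and the effects are illustrative. Groups are taken as equal; section 6.2 describes a 2:1 block strategy, but three places give 30 per group. There is no baseline adjustment. Section 6.4 also removes people who do not complete their allocated amount, so analysed numbers may be below the retained numbers.

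**Step 1: what the ANOVA responds to.** Power comes from the non-central F distribution with 3 and 4(n−1) df and λ = n × S, where S = Σ(μᵢ − μ̄)².

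- Means (0.8, 0.8, 0, 0): μ̄ = 0.4 and S = 4 × 0.16 = 0.64, so λ = 19.2 at n = 30.
- Means (0.5, 0, 0, 0): μ̄ = 0.125 and S = 0.1406 + 3 × 0.0156 = 0.1875, so λ = 5.625 at n = 30.

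| True means, Groups 1, 2, 3, 4 | G3−G4 | G2−G1 | Power n=30 | n=24 | n=18 |
|---|---|---|---|---|---|
| 0.8, 0.8, 0, 0 | 0 | 0 | 0.964 | 0.912 | 0.799 |
| 1.0, 0.5, 0, 0 | 0 | −0.5 | 0.975 | 0.931 | 0.829 |
| 0.5, 0, 0, 0 | 0 | −0.5 | 0.475 | 0.385 | 0.290 |
| 0.5, 0.5, 0.5, 0 | 0.5 | 0 | 0.475 | 0.385 | 0.290 |
| 0.5, 0.5, 0, 0 | 0 | 0 | 0.607 | 0.499 | 0.379 |
| 0.5, 0.3, 0.05, 0 | 0.05 | −0.2 | 0.416 | 0.335 | 0.254 |
| 0.8, 0.48, 0.08, 0 | 0.08 | −0.32 | 0.841 | 0.739 | 0.593 |
| 0.8, 0, 0, 0 | 0 | −0.8 | 0.894 | 0.805 | 0.664 |

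A simulation of 20,000 trials at n = 30 gave 0.965 for the first row and 0.478 for the third.

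Three comparisons matter:

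- Row 1: both aimed differences are zero, yet the test rejects in 96% / 91% / 80% of trials.
- Rows 1 and 2: rejection is almost equally likely whether 60% equals 100% or falls 0.5 SD short of it.
- Rows 3 and 4: power is identical whether the only effect is a shortfall of 60% against 100% (aim 2) or a benefit of 10% over none (aim 1). S is 0.1875 in both.

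**Step 2: what a non-significant result means.** In row 3, 60% is truly 0.5 SD worse than 100%. The ANOVA is then non-significant in 1 − 0.475, 1 − 0.385 and 1 − 0.290 of trials: 52% / 62% / 71%.

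**Step 3: what the data could say about Group 2 minus Group 1.** The 95% CI half-width is t × √(2/n).

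| n per group | √(2/n) | Half-width, four-group pooled df | Half-width, two-group df |
|---|---|---|---|
| 30 | 0.258 | 0.511 | 0.517 |
| 24 | 0.289 | 0.573 | 0.581 |
| 18 | 0.333 | 0.665 | 0.677 |

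An observed difference of zero would therefore not exclude a 0.5 SD loss. With the pooled df, Group 2 would have to outperform Group 1 by more than 0.511 − 0.5 = 0.011 SD at n = 30, 0.073 SD at n = 24 or 0.165 SD at n = 18 before that loss was excluded. The 0.5 SD is the protocol's MCID yardstick for DSMQ-R and PAID, used here as a benchmark and not as a proposed margin.

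**Step 4: would a formal similarity test be realistic here?** Take a margin of 0.5 SD, a true difference of zero and one-sided 2.5%. By normal approximation, non-inferiority power is 49% / 41% / 32%. For 80% power, n = 2 × (1.96 + 0.842)² / 0.5² = 62.8, so 63 per group; margins of 0.4 and 0.3 SD need 99 and 175.

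**The case against.** The strongest reply is that this is a feasibility study. Its aims are worded as exploration, its questionnaire outcomes are called preliminary, it is declared unpowered, and no progression criterion depends on the comparison. The ANOVA matches the one formal hypothesis and the one numbered question. All of that is true, and it limits the consequence. It does not close the gap: a study justified by estimating effects should say which effects, and an unpowered study is where a non-significant test says least.

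A second reply is that 6.4 goes beyond significance by planning MCID reporting, which bears on aim 1's clinical wording. But the MCID is not tied to Group 3 v Group 4 or to Group 2 v Group 1. For DSMQ-R and PAID it is derived from the trial's own data, so it is not a margin fixed in advance.

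Third, the 96% rejection rate is the ANOVA working correctly, because the global null is false in that case, and any omnibus test has power that varies with the pattern. This is correct. The figures show that the test answers a different question from the aims, not that it is invalid.

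Fourth, naming contrasts does not narrow the intervals, and at 30 per group 0.51 against 0.50 SD is a slim difference. Both points stand. The gain is that each aim receives its own estimate with its uncertainty shown.

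**Conclusion.** The concern holds. The stated test can be significant or non-significant without answering either aim, and no result from it can show that 60% is as effective as 100%. That follows from the form of the analysis and needs no assumed effect. The sizes in the working do rest on assumptions: equal groups, a common SD, no baseline adjustment and illustrative effects. Over the patterns examined at 30 per group, power runs from 0.416 to 0.975, with little relation to whether either aimed difference exists.

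This should be fixed before analysis. It affects the reporting of the aims and the estimates handed to the full trial, not the progression decision.

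**What to change.** In 6.4, keep the ANOVA for the global null and pre-specify two contrasts from the same model: Group 3 minus Group 4, and Group 2 minus Group 1. Report each as an estimate with a 95% CI for each outcome, with DSMQ-R first. State that p>0.05 will not be read as evidence that 60% is as effective as 100%. It would also help, though it is not essential, to read the DSMQ-R interval for Group 3 minus Group 4 against the MCID already planned, since aim 1 asks about clinical significance.

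In the Study Summary, the Rationale and section 5, reword aim 2 as estimating the difference between 60% and 100% completion. Leave any non-inferiority or equivalence test to the full trial, with a justified margin and direction fixed in advance for each outcome.

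The cost is wording in four places. The contrasts come from the same SPSS model and need no further participants or data. The price is a more modest aim 2. The contrasts would inherit the analysis set in 6.4, which excludes people who do not complete their allocated amount, so they should not be described as intention-to-treat estimates.
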